C.2.4. fMRI: MR scanning at WSU will be performed on a 3.0 Tesla Siemens Magnetom Verio System using an industry-leading 32-channel head-coil for superior image quality. We will use a multi-band EPI sequence [similar to: TR = 2000ms; TE = 30ms; Flip = 73°; 128x128 matrix; FOV = 256 mm; 66 slices; 2.0 x 2.0 x 2.0 mm voxels], which we are currently using in PI [name]'s K01 project. A high-resolution structural image will provide precise anatomical localization. Whole-brain fMRI blood oxygen-level dependent (BOLD)-related signal measures will be acquired to measure task- and drug-related effects and to minimize susceptibility artifact (signal loss) at the medial temporal lobe (including the AMYG and the vmPFC)¹³³⁻¹³⁵.

C.2.5. General Statistical Approach: All analyses will use a conventional alpha level of 0.05 and all tests will be two-tailed. To evaluate the main effects, Analysis of Variance will be used for neuroimaging (i.e., BOLD percent signal change (PSC)) and peripheral measures of fear (e.g., SCR, US expectancy, SUDS, psychological/mood measures). We will also include covariates such as gender and childhood trauma/adversity

if found unbalanced and correlated ($r > 0.03$) with the outcome variable (e.g., MANCOVA, ANCOVA). If significant, multivariate analysis will be followed by univariate analysis, which if significant, will be followed-up with simple effects analysis (e.g., independent t-tests, paired t-tests). In addition to omnibus tests, planned comparisons will be used to test specific hypotheses such as THC dose (vs. PBO) on fear extinction in PTSD, as well as comparisons between THC doses; if there is no significant difference between THC doses we will examine potential positive trends with increasing dose. To evaluate relationships, Pearson correlations will be used along with scatterplots to examine the nature of the relationships. Hochberg step-down multiplicity adjustment will be used to control for all multiple comparisons¹³⁶. Confidence intervals and effect sizes will be also be calculated.

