Specific Aim 1 (R61 Primary Target Engagement): Assess effects of THC on recall of extinction learning and vmPFC and/or HPC activation in PTSD patients in a dose-finding study. *Hypothesis 1A: Relative to PBO, THC will dose-dependently increase vmPFC and/or HPC activation to a CS+E (vs. CS+U) during proximal (24 hr post-extinction learning) and/or distal (1 week post-extinction learning) recall of extinction learning in PTSD.* PCS (CS+E vs. CS+U) with ROIs (vmPFC, HPC) will be submitted to MANCOVA with Group (PTSD-5mg, PTSD-10mg, PTSD-PBO, TEC) as between-subjects factor and Recall (24 hr, 1 week) as within-subject factor, controlling for potential confounds. In addition to omnibus tests, planned comparisons will examine dose of THC on prefrontal-limbic engagement during recall of extinction learning in PTSD relative to PBO, and comparisons between THC doses; if there is no significant difference between THC doses we will examine potential positive trends with increasing dose. Similar analyses will be conducted using other variables of interest such as psychological measures, mood state, and drug effects. *Hypothesis 1B: Relative to PBO, THC will dose-dependently decrease peripheral measures of extinction recall (“extinction recall index” (ETI), US expectancy, SUDS) to the CS+E during a proximal and/or a distal test of extinction learning recall in PTSD.* These data will be submitted to MANCOVA with Group (PTSD-5mg, PTSD-10mg, PTSD-PBO, TEC) as between-subjects factor and Recall (24 hr, 1 week) as within-subject factor, controlling for potential confounds. Analyses will be comparable to that used to examine BOLD activation (*Hypothesis 1A*). *Hypothesis 1C: vmPFC and/or HPC activation will correspond with extinction recall success (i.e. higher ETI, lower US expectancy, lower SUDS).* Pearson correlation analyses will be used to correlate measures of BOLD activation (PSC) and peripheral measures (e.g., SCR, ETI, US expectancy) to the CS+E vs. CS+U within and across the two contexts/recall and renewal tests.

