R61 Power Analysis: We have conducted several power calculations in our previously published work used to determine the sample sizes proposed here. First, we have consistently found that an *n* of 14-16 healthy controls and an *n* of 14-16 PTSD patients provide adequate power to observe: 1) SCR differences and AMYG, vmPFC, HPC signal differences between groups during fear extinction and/or extinction recall; and 2) THC's effects on ETI and AMYG, vmPFC, and HPC activation in healthy controls. Similarly, normalization of corticolimbic responsivity to affective stimuli has been observed following exposure-based therapy in an *n* of 14 anxious patients¹⁴⁸ and following administration of a serotonin selective reuptake inhibitor (SSRI) with an *n* of 21 anxious patients¹⁴⁹. Given that the effect sizes tested within- and between-groups in previous fMRI studies have ranged between moderate to large (Cohen *d* = 0.7 - 1.5) with the anticipated cohort of 20 participants per group (PTSD-5mg, PTSD-10mg, PTSD-PBO, TEC), who complete the entire protocol with usable fMRI and SCR data, will confer >80% power to detect an effect size 0.72 or higher after necessary multiplicity adjustment.

PROTECTION OF HUMAN PARTICIPANTS

This Human Participants Research meets the definition of a clinical trial.

1. Risks to Human Participants

a. Human Participants Involvement, Characteristics, and Design

Involvement of Human Participants:

The total time commitment estimated per participant is 8.5-13 hr across all study visits. This is broken down below:

Visit 1: Screening & Study Entry: Approximately 3 hours for participants, unless a participant has already completed any of the screening assessments as part of another separate study. In this case, if the overlapping screening assessments were completed no more than 1 month prior to Visit 1 and the participant has signed HIPPA Authorization allowing us to access this prior data, Visit 1 will be approximately 1.5 hr.

Note: Due to the length and rigor of this initial screening process, it may sometimes be necessary for participants to complete screening measures across more than one visit (e.g., schedule conflicts). All screening measures will be completed within 2 weeks of the consent date.

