Visit 2: Fear Acquisition: Approximately 1 hr for all participants. Participants are considered enrolled in the study once they have begun Visit 2 (if enrolled in PTSD group, participant will be randomized). Visit 2 will occur within 6 months of Visit 1. If more than 6 months have passed, we will re-do Visit 1 before the participant is able to complete visits 2 – 5.

Visit 3: Fear Extinction: Approximately 5 hr for those receiving a capsule (PTSD groups) or approximately 3 hours for those not receiving a capsule (TEC group)

Visit 4: Fear Extinction Recall and Fear Renewal Test (approximately 24 hr after extinction, but no more than 1 week later): Approximately 1.5 hr

Visit 5: Fear Extinction Recall, Fear Renewal Test, & Debriefing (approximately 1 week after extinction, but no more than 3 weeks later): Approximately 1.5 hr

Nature of Participant Population: Participants of both genders will be included in the study and the age range of participants will be from 18-60. Persons below 18 or above 60 are excluded because beyond this range age may influence response to the drugs. Furthermore, the relatively small age range is intended to reduce variation in performance on the behavioral task. There are no enrollment restrictions based upon race or ethnic origin. Candidates will undergo a structured clinical psychiatric interview¹⁵⁰ and complete questionnaires related to their general physical health, current medications, with a detailed section on current and lifetime drug and alcohol use. This study will not involve vulnerable populations.

The number of participants expected to participate is 104: 78 trauma-exposed participants with PTSD and 26 trauma-exposed participants without PTSD (TEC; demographically matched). There will be 3 experimental groups: PTSD participants will be assigned to 5mg of THC (n=26), 10mg of THC (n=26), or a placebo (PBO) (n=26). The 26 TEC participants will not receive THC or PBO. With the conservative anticipation 25% will fail to complete all parts of the study, we estimate 20 PTSD participants in each condition (60 PTSD participants in total) and 20 TEC participants will complete the study for a total of 80 participants. Participants will be recruited from the Detroit community and mental health clinics. We will enroll up to 175 participants to guarantee enough viable data and to account for participant drop out.

Recruitment

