Vulnerable Populations

This study will include women of child-bearing potential and college students. However, we will conduct urine pregnancy tests at the screening visit (Visit 1) and at the beginning of Visit 3 to make sure that women are not pregnant. Of note, if the participant is unable to provide a urine sample at Visit 1 (e.g., currently menstruating), we will conduct a urine pregnancy test at the beginning of visit 2. We will also conduct pregnancy tests if the study staff and/or participant have reason to believe they may be pregnant. In addition, participation of college students in this study is completely voluntary, as it is for all participants, and will not be required by any course.

Study Group Assignment

Individuals with PTSD will be randomized to a THC or PBO condition. In our previous studies we have shown that 7.5mg of THC facilitates extinction recall and modulates prefrontal and hippocampal activation in healthy humans volunteers^{55,113}. Moreover, PI [name] has preliminary data to suggest that 7.5mg of THC may facilitate extinction recall in PTSD, but it is not known whether this is the MED. This is an initial step in translation to be tested in the R61 phase. Therefore, we will have a low 5mg condition and a high 10mg condition should 5mg be too low to detect effects. Of note, a 10mg dose of THC does not typically produce anxiety¹⁵¹ or strong negative effects on cognition¹⁵². We aim to identify the MED that facilitates recall of extinction learning. Dronabinol is administered only by the oral route and will be placed in opaque capsules with dextrose filler. Placebo capsules will be identical in appearance but will contain only dextrose. All capsules will be administered to participants in double-blind conditions and participants assigned to receive dronabinol (two-thirds of the PTSD participants) will only receive dronabinol on one occasion.

Study medication, dronabinol or PBO, will be dispensed to participants by PI [name], who possesses a Schedule II-V controlled substance research license through the State of Michigan and the DEA and has experience in the use of dronabinol and PBO in human participant research. A registered pharmacist will handle

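### The stated power of more than 80% at an effect size of 0.72 does not hold for a THC dose against placebo: 20 versus 20 gives about 60% unadjusted and about 45–56% per contrast after Hochberg

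*Combined protocol and SAP*

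**What the plan says.** The R61 Power Analysis at the end of section C.2.9 assumes 20 participants per group (5 mg, 10 mg, placebo and trauma-exposed controls) with usable fMRI and SCR data. It says that this number "will confer >80% power to detect an effect size 0.72 or higher after necessary multiplicity adjustment". Cohen's d is the only metric named there, with a prior range of 0.7 to 1.5, and the text says that "effect sizes tested within- and between-groups in previous fMRI studies have ranged between moderate to large". The section on the participant population gives the same number of completers: "we estimate 20 PTSD participants in each condition (60 PTSD participants in total) and 20 TEC participants will complete the study".

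The tests that this power must support are set out elsewhere:

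- Section C.2 describes a between-subjects design.
- Section C.2.5 says "All analyses will use a conventional alpha level of 0.05 and all tests will be two-tailed", and "Hochberg step-down multiplicity adjustment will be used to control for all multiple comparisons".
- Under Specific Aim 1 in C.2.9, "planned comparisons will examine dose of THC on prefrontal-limbic engagement during recall of extinction learning in PTSD relative to PBO", "and comparisons between THC doses".

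The power paragraph does not name the test, the contrast, the number of comparisons in the Hochberg family, a correlation between the two recall visits, or a covariate R-squared.

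**The concern.** This is the only sentence that puts a power figure on the planned 20 per group, and it serves the primary aim of a dose-finding study. An effect of 0.72 lies near the lower end of the range the team cites, so it is a value they could meet in practice. Two independent groups of 20 are too few for 80% power at that effect, even with no adjustment.

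The practical risk lies in how a non-significant result is read. The study looks for the MED, and Study Group Assignment gives this reason for the higher arm: "Therefore, we will have a low 5mg condition and a high 10mg condition should 5mg be too low to detect effects". A reader who trusts the power sentence would expect a true effect of 0.72 at 5 mg to be missed less than 20% of the time. On the figures below it would be missed about 44–55% of the time after Hochberg, so a miss would say little about whether the dose is active.

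**Working it through.** **Inputs from the documents.** n = 20 per group (R61 Power Analysis); d = 0.72 (same place); two-sided alpha 0.05 and Hochberg (C.2.5); independent groups (C.2); contrasts 5 mg vs placebo, 10 mg vs placebo and 5 mg vs 10 mg (Aim 1). The size of the Hochberg family is not given, so results are shown for two contrasts (each dose vs placebo) and for three (adding dose vs dose).

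**Step 1: one contrast, no adjustment.** The noncentrality parameter is d × √(n/2) = 0.72 × √10 = 2.277, with 38 degrees of freedom. The two-sided 0.05 critical value is 2.024, and the noncentral t gives a power of **0.602**. The normal approximation gives Φ(2.277 − 1.960) = Φ(0.317) = 0.624. Pooling the error over three or four groups (57 or 76 df) gives 0.610 or 0.613. The stated figure is not reproduced.

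**Step 2: Bonferroni, as a reference.** The same noncentrality is used.

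| Tests | Critical t | Power |
|---|---|---|
| 2 | 2.334 | 0.484 |
| 3 | 2.505 | 0.420 |
| 12 | 3.049 | 0.239 |

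**Step 3: Hochberg.** Simulated with 200,000 runs and a shared placebo arm. Small differences between runs and between separate and pooled error account for the ranges.

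| True effects | Family | Power per active dose vs placebo |
|---|---|---|
| Both doses 0.72 | 2 | 0.55–0.56 |
| Both doses 0.72 | 3 | 0.45–0.47 |
| One dose 0.72, other 0 | 2 | 0.49–0.50 |
| One dose 0.72, other 0 | 3 | 0.45–0.46 |

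With two contrasts and both doses active, the chance of rejecting at least one is about 0.67 and of rejecting both is 0.44.

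If the two ROIs and two visits also belong to the family, all dose-vs-placebo effects are 0.72 and the assumed correlation is 0.3–0.7, power per test is 0.37–0.39 for 8 tests (2 doses × 2 ROIs × 2 visits). It is 0.26–0.27 for 12 tests, which adds dose vs dose.

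**Step 4: what 20 per group can detect.** Solving for d at 80% power gives 0.91 at 0.05, 1.01 at 0.05/2 and 1.06 at 0.05/3. Under Hochberg with equal effects at both doses it is about 0.94 (two contrasts) and 1.02 (three). Conversely, 80% power at d = 0.72 would take 32, 38 and 42 per group at those three alpha levels.

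**Step 5: other readings that might recover the figure.**

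- One-sided test: 0.72.
- All 26 per arm, no dropout: 0.72 unadjusted, 0.61 at 0.025.
- Both doses pooled, 40 vs 20: 0.73 unadjusted.
- Four-group omnibus ANOVA with f = 0.36: 0.75.
- Mean of the two recall visits, effect 0.72/√((1+ρ)/2), Hochberg over two contrasts: 0.87, 0.79, 0.69 and 0.63 at assumed ρ = 0, 0.2, 0.5 and 0.7.
- Covariates, effect 0.72/√(1−R²), Hochberg over two contrasts: 0.72, 0.79 and about 0.87 at assumed R² = 0.3, 0.4 and 0.5.
- At least one rejection among 8 tests (doses × ROIs × visits): 0.81, 0.75 and 0.68 at assumed correlation 0.3, 0.5 and 0.7.
- Within-group paired test, n = 20: noncentrality 0.72 × √20 = 3.220, critical value 2.093, power 0.863 unadjusted. Under Hochberg over 2 to 4 groups it is 0.82–0.85.

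**The case against.** The strongest reply is that the sentence is not tied to a dose-vs-placebo contrast. It names no test, and its source effect sizes mix within-group and between-group results. Paired comparisons and a CS+E versus CS+U factor are in the plan, and for a within-group test with 20 people the stated power is attainable (86% unadjusted, 82–85% after Hochberg). This stands as a possible origin of the figure. It does not rescue the sentence for Aim 1, because a within-group test does not compare THC with placebo.

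A second reply is that Hypothesis 1A accepts an effect in either ROI and at either recall visit, so power per single test understates the chance of supporting the hypothesis. This is fair. For one dose, counting at least one rejection among 4 tests (2 ROIs × 2 visits, Hochberg over 4, all effects 0.72), power is about 0.82 at correlation 0.1, 0.79–0.80 at 0.2, 0.70 at 0.5 and 0.63 at 0.7. It reaches 80% only when the four measures are nearly uncorrelated, and the plan states no correlation.

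Third, the family sizes used here are assumptions, and dose evaluation also draws on omnibus tests, trends, effect sizes and confidence intervals. No rule says that a non-significant 5 mg result settles the dose. These points limit how far the consequence can be pressed. They do not affect the unadjusted 60%, which depends on no choice of family.

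**Conclusion.** The concern holds. For a single THC-vs-placebo comparison at d = 0.72 with 20 per group, two-sided, power is about 60% before adjustment. After Hochberg it is about 55–56% (two contrasts) or 45–47% (three) if both doses have that effect, and about 45–50% if only one does. These figures assume a two-sample comparison of one outcome at one visit with no covariate gain.

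More than 80% can be had by a within-group test, by nearly uncorrelated visits or ROIs, or by covariates explaining more than about 40% of the variance. The first is not the drug comparison, and the plan states no values for the others. The conclusion is therefore about the dose-vs-placebo contrasts and not about every test in the plan. For those contrasts the sentence is wrong as written and should be corrected.

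**What to change.** In the R61 Power Analysis, state the test, the contrast, the size of the Hochberg family and any assumed visit correlation or covariate R-squared behind 0.72, and then restate the claim. Suggested wording:

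> With 20 completers per group, a two-sided between-group comparison has 80% power for d of about 0.91 unadjusted, and about 1.01 (two contrasts) or 1.06 (three contrasts) at the conservative Bonferroni level. At d = 0.72, power is about 60% unadjusted and about 46–56% per dose-versus-placebo contrast after Hochberg over three or two contrasts when both doses have that effect.

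If ROIs and visits belong to the family, give the figure for that family. If the team has a model that does yield more than 80%, the same edit is the place to show it.

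The cost is one or two sentences, a less favourable number, and a decision on what the Hochberg family contains. No additional participants and no change to the design or procedures are requested.

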C.2. Overall Study Design: The R61 study will employ a randomized, double-blind, PBO-controlled, between-subjects design, coupling a standard Pavlovian fear conditioning paradigm during fMRI with an acute pharmacological challenge using oral dronabinol (THC) or PBO *prior to fear extinction* in PTSD patients and test recall of extinction learning 24 hr (proximal memory) and 1 week later (distal memory) when spontaneous recovery is expected to be robust. 78 PTSD participants will be randomized to 1 of 3 conditions: single doses of 5mg or 10mg of THC, or PBO, using covariate adaptive randomization¹¹⁸⁻¹²², in which a new participant is sequentially allocated to a treatment condition by taking into account baseline characteristics (e.g., CAPS-5, age, sex, race) and previous assignments of participants¹²³, with 26 PTSD participants per condition. However, because randomization does not guarantee comparability across groups, the groups will be compared to ensure reasonable similarity in the distributions of their baseline characteristics. The imbalance in covariate levels will be measured by a χ^2 goodness-of-fit test (for categorical covariates) or t-test (for quantitative covariates). Variables with significant group differences ($p<0.05$) will be included as covariates in primary analyses. Additionally, 26 healthy trauma-exposed controls (TEC; demographically matched) will be included and tested at comparable time points to separate the impact of trauma from the impact of PTSD. The TEC group will not receive THC, any drug-related monitoring, or undergo blood draws but will otherwise complete all phases of the

experiment. With the conservative anticipation that about 25% will fail to complete all parts of the study, we estimate about 20 PTSD subjects in each condition (60 PTSD participants in total) and 20 TEC participants in total. Participants will be recruited from the Detroit community and mental health clinics (**see 'Protection of Human Participants'**).

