Key inclusion criteria: All participants must be age 18-60, able to consent to the study, generally medically and neurologically healthy, and endorse exposure to a Criterion A stressor (defined by clinician-administered PTSD scale for DSM-5; CAPS-5). In addition, PTSD candidates must have significant PTSD severity as indicated by a clinician-administered PTSD scale for DSM-5 (CAPS-5) diagnosis and/or score of ≥ 25 regardless of trauma type as effect size of PE has been shown to be similar across trauma types (i.e., combat/terror, childhood sexual abuse, rape, mixed¹²⁴). TECs must be free of any history of PTSD symptoms (CAPS-5 score < 25 and no diagnosis). **Key exclusion criteria:** Participants in either group with the following are excluded from the study: a) clinically significant medical or neurologic condition; b) MRI contraindications (metal objects in body or claustrophobia); c) positive urine pregnancy test or self-reported current pregnancy identified during screening procedures; d) pervasive development disorder history; e) traumatic brain injury (TBI) with current cognitive impairment related to TBI; f) exclusively left-handedness; g) current severe alcohol or substance use; h) risk of harm to self or others that requires immediate intervention; i) lack of fluency in English; j) current or past diagnosis of bipolar, schizophrenia, or psychotic disorder; or k) presence of contraindications, current or past allergic or adverse reaction, or known sensitivity to cannabinoid-like substances. In addition, PTSD participants with the following will be excluded: a) comorbid mood or anxiety disorder that is *primary* to PTSD (i.e. when treatment is indicated for symptoms beyond PTSD such as major depressive disorder, which does not involve exposure to fears¹²⁵); b) concomitant treatment with medication that has level 1 evidence indicating severe drug-drug interactions with dronabinol that is taken daily. (**see c'Protection of Human Participants'**). TEC's with current diagnoses of any obsessive-compulsive, trauma/stressor-related, depressive, or anxiety disorder will be excluded.

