Inclusion criteria for the PTSD group will be: (a) significant PTSD severity as indicated by a clinician-administered PTSD scale for DSM-5 (CAPS-5) diagnosis and/or score (see below) of ≥ 25 of at least the past month prior to study entry (primary PTSD will be identified as the patient's primary concern). *Inclusion criteria for the TEC group will be:* (a) absence of any history of PTSD symptoms (CAPS-5 < 25 and/or no diagnosis), related to any type of trauma.

Exclusion Criteria

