Exclusion criteria across groups will be: (a) exclusively left-handed (i.e., score of -100.00 on Handedness Questionnaire); (b) risk of harm to self or others that requires immediate intervention; (c) presence of contraindications, current or past allergic or adverse reaction, or known sensitivity to cannabinoid-like substances (dronabinol/marijuana/cannabis/THC, cannabinoid oil, sesame oil, gelatin, glycerin, and titanium dioxide); (d) lack of fluency in English; (e) currently pregnant (positive pregnancy test or self-report), planning pregnancy, or lactating (women); (f) traumatic brain injury (as defined by The American Congress of Rehabilitation as a person who has had a traumatically induced physiological disruption of brain function (i.e., the head being struck, the head striking an object, and/or the brain undergoing an acceleration/deceleration movement (i.e., whiplash) without direct external trauma to the head), as manifested by at least one of the following: any loss of consciousness; any loss of memory for events immediately before or after the injury; any alteration in mental status at the time of the incident; or focal neurological deficits that may or may not be transient); (g) inability to tolerate small, enclosed spaces without anxiety (e.g. claustrophobia), as determined by self-report; (h) presence of ferrous-containing metals within the body (e.g., aneurysm clips, shrapnel/retained particles); (i) current or past diagnosis of any bipolar or related disorder or schizophrenia spectrum and other psychotic disorder as determined by the MINI 7.0.2; (j) current severe alcohol or substance use as determined by the MINI 7.0.2; (k) history of pervasive developmental disorder (e.g., Autism, Asperger syndrome). *Exclusion criteria for the PTSD group will be:* (a) current diagnosis of a mood, anxiety, or other disorder that is more clinically salient than PTSD (e.g., MDD, OCD, Panic, GAD); (b) concomitant treatments with medication known to have level 1 evidence for severe drug- drug interactions with dronabinol that are taken daily. *Exclusion criteria for the TEC group will be:* (a) current diagnosis of any obsessive-compulsive and related disorders or trauma- and stressor-related disorders as determined by the MINI 7.0.2 for DSM-5; (b) current diagnosis of any depressive disorder as determined by the MINI 7.0.2 and a score > 22 (indicating very severe depression) on the Hamilton Depression Scale (HAM-D); (c) current diagnosis of any anxiety disorder as determined by the MINI 7.0.2 and a score > 24 (indicating moderate to severe anxiety) on the Hamilton Anxiety Scale (HAM-A).

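### The control-group entry rules contradict each other and overlap with PTSD entry, and the omnibus test for Hypotheses 1A and 1B includes this non-randomised group

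*Combined protocol and SAP*

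**What the plan says.** **Eligibility.** The TEC rule appears twice.

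- Section C.2, key inclusion criteria: "TECs must be free of any history of PTSD symptoms (CAPS-5 score < 25 and no diagnosis".
- Protection of Human Participants, Inclusion Criteria: "absence of any history of PTSD symptoms (CAPS-5 < 25 and/or no diagnosis), related to any type of trauma".

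The second of these sections admits people to the PTSD group on a CAPS-5 "diagnosis and/or score (see below) of ≥ 25 of at least the past month prior to study entry". C.2 likewise accepts a diagnosis, a score of at least 25, or both.

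The TEC exclusions also appear twice.

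- C.2: "TEC's with current diagnoses of any obsessive-compulsive, trauma/stressor-related, depressive, or anxiety disorder will be excluded".
- Exclusion Criteria under Protection of Human Participants: "current diagnosis of any depressive disorder as determined by the MINI 7.0.2 and a score > 22" on the HAM-D, and "current diagnosis of any anxiety disorder as determined by the MINI 7.0.2 and a score > 24" on the HAM-A. That list also excludes current "trauma- and stressor-related disorders as determined by the MINI 7.0.2 for DSM-5", with no severity threshold.

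**Analysis.** C.2 includes the TEC group "to separate the impact of trauma from the impact of PTSD". It is not randomised and receives neither THC nor placebo. For Hypotheses 1A and 1B, C.2.9 specifies a MANCOVA with Group at four levels (5 mg, 10 mg, placebo, TEC) and Recall as the within-subject factor. Planned comparisons of each dose with placebo, and of the doses with each other, come on top of the omnibus. C.2.5 applies a Hochberg adjustment, and it makes univariate and simple-effects follow-up depend on a significant multivariate result.

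**The concern.** There are two separate points.

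**A. Who is a control.** Screeners cannot follow both texts. Under one of them, a person with a PTSD-level score and no diagnosis can be entered in either group. A candidate with a current depressive disorder and a HAM-D of 20 is excluded by C.2 and allowed by the later list. Controls with PTSD-level scores or a current mood or anxiety disorder blur the one contrast for which TEC was added.

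**B. What the omnibus tests.** Hypotheses 1A and 1B are about THC relative to placebo within PTSD. A four-level Group effect can be significant only because PTSD differs from TEC. The plan has reason to expect such a difference: sections A.3 and C.1 cite lower vmPFC and HPC activation in PTSD than in trauma-exposed controls at extinction recall, which is the Hypothesis 1A outcome. A significant Group effect could then be reported as support for a THC hypothesis, and it would open the follow-up path in C.2.5.

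**Working it through.** The plan gives no figure for either point, so there is none to reproduce.

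**Step 1. Cross-tabulate the entry rules** by CAPS-5 score and PTSD diagnosis.

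| CAPS-5 | Diagnosis | PTSD entry | TEC, Inclusion Criteria (*and/or*) | Same, after the MINI trauma/stressor exclusion | TEC, C.2 (*and*) |
|---|---|---|---|---|---|
| < 25 | no | no | yes | yes | yes |
| < 25 | yes | yes | yes | no | no |
| ≥ 25 | no | yes | **yes** | **yes** | no |
| ≥ 25 | yes | yes | no | no | no |

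The groups overlap in 2 cells on the *and/or* wording, in 1 after the MINI exclusion (if MINI and CAPS-5 agree on diagnosis), and in 0 under C.2.

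**Step 2. Effect of misplaced controls on PTSD-placebo versus TEC.** Inputs: 20 completers per group and d from 0.7 to 1.5 (R61 Power Analysis); two-sided 5% (C.2.5). The documents do not say how many people fall in the overlap cell, so 2, 4 or 6 of 20 controls are assumed to come from the PTSD distribution.

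- Mean shift alone: effective d = d × (1 − k/20), noncentrality = effective d × √(20/2), 38 df, critical t = 2.024. At d = 1.0 with k = 2, 0.90 × 3.162 = 2.846, which gives 79% power.
- Simulation, which also carries the extra spread in a mixed group:

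| True d | k = 0 | k = 2 | k = 4 | k = 6 |
|---|---|---|---|---|
| 0.7 | 58% | 48% | 39% | 31% |
| 1.0 | 87% | 78% | 67% | 54% |
| 1.5 | 99.6% | 98% | 94% | 85% |

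At d = 1.0 the mean shift alone gives 79%, 69% and 58%.

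**Step 3. The omnibus when THC does nothing.** Take one outcome, 20 per group, group means (0, 0, 0, D) with TEC last, and unit SD. Noncentrality = 20 × [3 × (D/4)² + (3D/4)²] = 15D², with 3 and 76 df. At D = 0.7 this is 15 × 0.49 = 7.35. At D = 1.0 it is 15, and at D = 1.5 it is 33.75.

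| TEC shift D | Four-group omnibus rejects | Rejects with neither dose-vs-placebo contrast significant | Three-arm omnibus rejects |
|---|---|---|---|
| 0.7 | 59% | 54% | 5% |
| 1.0 | 90% | 85% | 5% |
| 1.5 | 99.9% | 95% | 5% |

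Smaller shifts of 0.3 and 0.5 give 13.6% and 32.2% for the four-group omnibus. A two-ROI version (Wilks' lambda, TEC shifted in both ROIs, assumed ROI correlation 0.3 to 0.7) rejects in 53–66%, 88–96% and 99.9–100% at D = 0.7, 1.0 and 1.5.

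**Step 4. The contrasts themselves.** In the same simulations, the chance of any false dose-versus-placebo claim after Hochberg adjustment of the two contrasts is 4.8%. It is 4.6–4.8% if the contrasts are tested only after a significant omnibus.

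**The case against.** **On A.** The words before the bracket ask for no history of PTSD symptoms, and on a plain reading a score of 25 or more fails that. This does not settle the matter. C.2 puts the same words before a bracket that accepts any score below 25, so they cannot mean no symptoms at all, and the bracket is the only part a screener can apply. It is also fair that the trauma/stressor exclusion covers more than PTSD, so it would remove some people in the overlap cell. It does not act on the score itself, so the cell stays open.

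The contamination shares have no source in the documents, and drawing these people from the full PTSD distribution is severe because they lack a diagnosis. If they sit halfway between the groups, which is equally an assumption, power at d = 1.0 is about 83%, 79% and 74%. The HAM-D and HAM-A discrepancy has not been sized. The affected contrast is not a named hypothesis, and the randomised comparison of THC with placebo is untouched. All of this limits the consequence; the texts still conflict.

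**On B.** A four-group model with planned contrasts is a common way to carry a reference group. Here the contrasts within the randomised arms are the test of THC, and they control error. That stands: the plan does contain a valid THC test. The remaining problem is that the omnibus is listed under Hypotheses 1A and 1B without a statement of what its Group effect means. It is also true that no PTSD-versus-TEC effect size is given. The range 0.7 to 1.5 is the plan's general range for earlier fMRI studies, and a smaller true shift makes the problem smaller.

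**Conclusion.** Both points hold.

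**A.** The plan contains two TEC inclusion rules and two sets of TEC exclusions that cannot both be applied. One inclusion rule lets a person with a CAPS-5 score of at least 25 and no diagnosis qualify for either group. How often this would happen is unknown. The loss of power in PTSD-placebo versus TEC rests on assumed shares of 10% to 30% and on how PTSD-like those people are.

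**B.** The four-level Group effect is not by itself evidence about THC. With inert THC and a TEC shift within the plan's own effect range, it is significant in 59% to 99.9% of trials, mostly with no significant dose contrast. These figures are stand-ins for the planned repeated-measures MANCOVA, with one summary score per outcome and no covariates.

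Neither point inflates false claims from the dose-versus-placebo contrasts or biases the randomised comparison. The risk is a blurred reference group and a misread omnibus. The plan should correct both before the analysis, but neither undermines the trial's main comparison.

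**What to change.** 1. Reconcile C.2 with the Inclusion and Exclusion Criteria under Protection of Human Participants into one TEC inclusion rule that makes the groups mutually exclusive (the *and* in C.2 does this) and one list of depressive and anxiety exclusions. State how controls already enrolled were classified, if there are any.
2. In C.2.9, run the Hypothesis 1A and 1B omnibus in the three randomised PTSD arms, with a 2-df Group effect and the planned contrasts. Report PTSD-placebo versus TEC separately, labelled as non-randomised, and say whether it belongs to the Hochberg family; if it joined the family of THC contrasts, it could cost them power.
3. If the four-group model is kept, add a sentence saying that its Group effect is not evidence about THC and that both hypotheses rest on the dose-versus-placebo contrasts.

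The cost is wording in the eligibility sections and one or two lines in C.2.9. Dropping TEC from the model takes the error df from 80 − 4 = 76 to 60 − 3 = 57. The two-sided 5% critical t moves from 1.992 to 2.002, and unadjusted power of one dose-versus-placebo contrast at d = 0.72 moves from 61.3% to 61.0%. (That these figures lie below the power stated in the R61 Power Analysis is a separate matter.)
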